10.2 ANALYSIS POPULATIONS

10.2.1 SAFETY POPULATION

The safety analysis population will contain all randomized subjects wherein treatment is attempted. The attempt is defined as the OMNI device or [REDACTED] touching the study eyes even if the procedure is not completed. Subjects will be grouped according to actual treatments.

10.2.2 INTENT TO TREAT (ITT) AND AS TREATED (AT) POPULATIONS

The Intent to Treat (ITT) analysis population will include all subjects randomized and grouped according to randomization assignment (as randomized) regardless if the assigned procedure is performed. The As Treated (AT) population will consist of the subjects that undergo the assigned procedure and will be grouped according to actual treatments. For this study, the AT population will be used for the primary analyses of

the primary and other effectiveness endpoints. The effectiveness analyses may be performed for the ITT population if needed.

10.3 DEMOGRAPHICS AND BASELINE CHARACTERISTICS

Subject demographics (age, race/ethnicity and gender) will be summarized by study group for the ITT, AT, and Safety populations using descriptive statistics. Age will be summarized as a continuous variable and categorized into the four groups based on the observed quartiles.

The baseline medicated IOP and washout (unmedicated) IOP will be summarized by study groups for the ITT and AT populations. They will be treated as continuous variables. The number of glaucoma medications in use at enrollment will be prepared for each of the study groups using descriptive statistics for categorical variables.

Medical and Ocular history will be summarized for each study group by number and percentage of subjects in the ITT and AT population.

For the Safety Population, ITT, and AT populations, subject accountability will be prepared based on Table G.1 of ANSI Z80.27-2014.

10.4 EFFECTIVENESS ENDPOINTS AND ANALYSIS METHODS

Descriptive statistics on continuous variables will include mean, standard deviation, median, minimum, and maximum. Confidence intervals for change from baseline will be included for selected endpoints. Categorical variables will be summarized using frequency counts and percentages. Exact confidence intervals for point estimates may be provided. Statistical testing will be one-sided with a significance level of 0.025 or two-sided significance level of 0.05 unless specify otherwise. Data listings of individual subject data may be provided.

10.4.1 PRIMARY EFFECTIVENESS ENDPOINT

The primary analysis of the primary effectiveness endpoint will be based on the AT population. The Baseline unmedicated DIOP will be used to impute the 12-month unmedicated DIOP for the subjects meeting any of the following criteria:

- Ocular hypotensive medications cannot be washed out properly at 12 months due to safety reasons.
- Have secondary surgical interventions (such as laser procedure or MIGS) to control IOP before the 12-month washout.
- Have any ocular procedures that can affect the IOP before the 12-month washout.

- Have IOP below 6 mmHg at 1 month or later
- Do not have the 12-month washed out DIOP due to any other reasons.

The change in unmedicated DIOP from baseline at 12 months will be calculated for each study eye as change = (12-month unmedicated DIOP – Baseline unmedicated DIOP).

The descriptive statistics (such as mean, standard deviation, median, minimum, and maximum) of the medication-free mean diurnal IOP and the change from baseline and the 95% confidence interval of the mean will be calculated for each of the three study groups. A two-sample t-test with a one-sided significance level of 0.025 will be used to compare the mean unmedicated DIOP change from baseline at 12 months for Hypotheses I and II described in Section [10.1](#). The two-sided 95% confidence interval based on the t-distribution will also be provided for the mean difference. In order to assess the pattern of the distribution, box-plots will be prepared for the medication-free mean diurnal IOP and its change from baseline for each of the three study groups.

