8.10 MANAGEMENT OF IOP AFTER SURGERY

In general, the primary consideration for the reintroduction of hypotensive medication is the preservation of the retinal nerve fiber layer, optic nerve and visual field.

[REDACTED] Administration of glaucoma medication in subjects with IOP < 21 mmHg will be considered on a case-by-case basis by the study Investigator and the sponsor.

No more than one ocular hypotensive agent should be added at a single visit or within a 2-week period, without prior approval of the sponsor.

In the event of a steroid response increase in IOP due to prolonged anti-inflammatory regimen, the guidelines above to treat increase in IOP should be followed; however, topical hypotensive medications should be discontinued once the topical steroid has been discontinued.

Since the study population is undergoing angle surgery involving use of an ophthalmic viscoelastic agent, which is known to cause IOP spikes in some patients in the immediate postoperative period, use of glaucoma medications in the first month after surgery will be allowed at the discretion of the study Investigator. This short-term use of glaucoma medications in the immediate postoperative period will not be considered "rescue therapy" and will not be considered in the effectiveness analyses for the study.

For subject safety, a change in medical therapy may be implemented or additional surgical measures may be performed at any time during the study at the Investigator's discretion in the event it is required. The primary concern of the Investigator and

Sponsor at all times is the health and safety of the subjects. Usage of hypotensive medications specifically indicated for prevention of IOP spikes following Nd:YAG capsulotomy and administered for up to 72 hours after Nd:YAG capsulotomy will not be considered rescue therapy.

Medications which have been re-started by the Investigator may be discontinued if the Investigator's judgment is that the target intraocular pressure has been reached and the continued use of some or all of the therapy may not be required. Discontinuation of medications after re-introduction is recommended to be in the reverse order of re-introduction. The rationale for discontinuation should also be documented in the subject's medical record.

A record of all ocular hypotensive medications added, discontinued or changed will be documented on the appropriate CRF for each scheduled visit or on a CRF for an Unscheduled Visit, if necessary.

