Another potential reason for intervention is hypotony. Intervention should only be considered if the hypotony has caused or is likely to cause sequelae such as a flat chamber or retinal detachment. No intervention is indicated when the vision is unchanged from screening, there is no persistent choroidal detachment, the anterior chamber is not flat with lens corneal touch, or the patient is asymptomatic. No intervention should be undertaken for hypotony which is not causing, or threatening to cause, a reduction in vision.

Secondary IOP-Lowering Interventions to Control IOP

If the subject requires another glaucoma procedure to control their IOP, the subject should continue to be followed according to standard of care until the adverse event resolves or 1-month post-re-intervention, whichever is longer. Following this, the subject should be withdrawn from the study.

Subjects who have had a secondary IOP-lowering intervention will be considered treatment failures for the purpose of the endpoint analyses. For the primary effectiveness endpoint of the study, the corresponding baseline unmedicated DIOP will be used to impute the 12-month unmedicated DIOP. These subjects will be included in the Safety Endpoint analyses through their withdrawal from the study.

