10.4.5 ADDITIONAL EFFECTIVENESS ANALYSES

The analyses described in this section are exploratory in nature. All the analyses will be based on the observed data of the AT population by the three study groups.

- Count and percent of subjects with the following DIOP change from baseline to 12 months stratified by the use of ocular hypotensive medication and/or SSI that can affect the IOP:
 - 40% ≤ Change (i.e. increase ≥ 40%)
 - 30% ≤ Change < 40% (i.e. 30% ≤ increase < 40%)
 - 20% ≤ Change < 30% (i.e. 20% ≤ increase < 30%)
 - 10% ≤ Change < 20% (i.e. 10% ≤ increase < 20%)
 - 0% < Change < 10% (i.e. 0% < increase < 10%)
 - Change = 0% (i.e. no change)
 - 10% < Change < 0% (i.e. 0% < decrease < 10%)
 - 20% < Change ≤ -10% (i.e. 10% ≤ decrease < 20%)
 - 30% < Change ≤ -20% (i.e. 20% ≤ decrease < 30%)
 - 40% < Change ≤ -30% (i.e. 30% ≤ decrease < 40%)
 - 50% < Change ≤ -40% (i.e. 40% ≤ decrease < 50%)
 - Change ≤ -50% (i.e. decrease ≥ 50%)
- Count and percent of subjects with the following DIOP 12 months stratified by the use of ocular hypotensive medication and/or SSI that can affect the IOP:
 - ≥6 mmHg to ≤ 21 mmHg
 - ≥6 mmHg to ≤ 18 mmHg
 - ≥6 mmHg to ≤ 15 mmHg
 - ≥6 mmHg to ≤ 12 mmHg
- IOP, IOP change, and IOP percent change from baseline at each visit (excluding use of ocular hypotensive medication and/or SSIs that can affect the IOP)
- The number of ocular hypotensive medications and change in the number of ocular hypotensive medications from screening to each post-operative

examination (including at 12 months prior to washout) excluding subjects treated with SSIs that can affect the IOP.

- The survival analysis (Kaplan Meier curve) with the log-rank test for the time to the first secondary surgery intervention (SSI) for controlling the IOP.
- The survival analysis with the log-rank test for the time to the first ocular hypotensive medications at or after 1 month postoperative. The analysis will include the cases with medications taken before 1 month and ongoing after 1 month.
- The survival analysis with the log-rank test for the time to the first SSI or the first ocular hypotensive medications at or after 1 month postoperative, whichever comes first.

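### As worded, the third baseline-imputation criterion in 10.4.1 overwrites a measured 12-month washed-out DIOP after any procedure able to affect IOP, and would include Nd:YAG capsulotomy for PCO

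*Combined protocol and SAP*

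**What the plan says.** Section 10.4.1 opens its imputation rule with "The Baseline unmedicated DIOP will be used to impute the 12-month unmedicated DIOP for the subjects meeting any of the following criteria" and then lists five criteria. Three of them matter here:

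- The second: "Have secondary surgical interventions (such as laser procedure or MIGS) to control IOP before the 12-month washout".
- The third: "Have any ocular procedures that can affect the IOP before the 12-month washout".
- The fifth: "Do not have the 12-month washed out DIOP due to any other reasons".

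Section 8.10 discusses "hypotensive medications specifically indicated for prevention of IOP spikes following Nd:YAG capsulotomy". It says that such drops, given for up to 72 hours, do not count as rescue therapy. It does not mention how the procedure is to be handled in the primary analysis. Under its heading on secondary interventions, the same section states: "Subjects who have had a secondary IOP-lowering intervention will be considered treatment failures for the purpose of the endpoint analyses". It prescribes baseline imputation for those subjects and withdraws them from the study after a period of follow-up.

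Section 10.4.2 limits the tipping-point analysis to subjects without a 12-month value for reasons outside the first four criteria. Section 10.4.3 keeps the primary imputation. Section 10.4.4 analyses the other effectiveness endpoints on available data of the As Treated population and calls those analyses exploratory.

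**The concern.** The second criterion already takes care of procedures done to control IOP, and the fifth takes care of absent values. What the third adds is procedures done for some other reason, including those in eyes that do have a 12-month washed-out DIOP. It asks only whether the procedure is able to affect IOP. It does not ask whether an effect could still be present at the 12-month measurement.

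Every treated eye has cataract extraction, and Appendix A (19.7) has PCO evaluated at the slit-lamp examination. Capsulotomy for PCO is therefore a foreseeable event in this population, although the documents do not say how often it occurs before month 12. A subject who has one is not withdrawn under 8.10, which withdraws those needing another glaucoma procedure. A measured 12-month value would normally exist, and the third criterion would replace it with baseline.

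At stake is the primary comparison for both hypotheses. Zeros that do not reflect the study procedure dilute the contrast and add variance.

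**Working it through.** **Does the wording reach capsulotomy?**

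1. The lead-in to 10.4.1 applies to subjects meeting any criterion, not only to subjects with a missing value.
2. The words of the fifth criterion might suggest that the first four are also reasons for a missing value. The fourth criterion (IOP below 6 mmHg at 1 month or later) does not make the 12-month value missing, so that reading does not hold for the list as a whole.
3. Section 8.10 refers to IOP spikes after Nd:YAG capsulotomy. On the protocol's own words, it is a procedure able to affect IOP.
4. The 72-hour provision concerns the drops and the rescue-therapy label. No visible text takes the procedure out of the third criterion.

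**What happens to one eye?** The Synopsis (inclusion criterion 5) gives baseline unmedicated DIOP of 24 to 39 mmHg. An eye that reaches 18 mmHg, the upper limit of the protocol's 6 to 18 mmHg endpoint, has fallen by at least 24 - 18 = 6 mmHg, and by 39 - 18 = 21 mmHg from the top of the range. The primary analysis would enter 0. On available data under 10.4.4, the same eye could count as a responder with a reduction of 20% or more.

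**The plan's sample size.** 411 / 3 = 137 completers per arm; 137 / 0.90 = 152.2, rounded up to 153; 3 x 153 = 459, as stated. The SD, effect and power are not visible. At one-sided 0.0125 and a difference of 1.5 mmHg, a t-test needs exactly 137 per arm with SD 4.0 at 80% power, or with SD 3.5 at 90%. SD 4 is therefore compatible with the design but remains an assumption.

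**Effect on the comparison.** Assumptions: mean change -8 mmHg, SD 4, a share q of eyes affected in both arms, and capsulotomy unrelated to IOP response. A share q of values becomes 0, so:

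- observed difference = (1 - q) x true difference
- observed SD = sqrt[(1 - q) x 4² + q(1 - q) x 8²]
- standardised-effect factor = (1 - q) x 4 / observed SD

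| q | Variance | SD | Factor | A true 1.5 mmHg reads as |
|---|---|---|---|---|
| 2% | 15.68 + 1.25 = 16.93 | 4.12 | 0.95 | 1.47 |
| 5% | 15.20 + 3.04 = 18.24 | 4.27 | 0.89 | 1.43 |
| 10% | 14.40 + 5.76 = 20.16 | 4.49 | 0.80 | 1.35 |

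**Power and error rate.** Normal approximation, 137 per arm, one-sided 0.0125 (critical value 2.241), SE = observed SD x sqrt(2/137). Non-inferiority is taken in its intended direction.

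- Superiority power = Φ[1.5(1 - q)/SE - 2.241]
- Non-inferiority power, arms truly equal = Φ[1.5/SE - 2.241]
- Non-inferiority type I error, true deficit 1.5 mmHg = Φ[1.5q/SE - 2.241]

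| q | SE | Superiority power | Non-inferiority power, equal arms | Non-inferiority type I error |
|---|---|---|---|---|
| 0% | 0.483 | 81% | 81% | 0.0125 |
| 2% | 0.497 | 76% | 78% | 0.015 |
| 5% | 0.516 | 70% | 75% | 0.018 |
| 10% | 0.543 | 60% | 70% | 0.025 |

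Section 10.4.1 states a one-sided level of 0.025, which differs from the per-hypothesis level in 10.1. That is a separate matter. At 0.025 the type I error with q = 10% is about 0.046. Over mean changes of -6 to -9 mmHg and SD 3.5 or 4.0, the q = 10% type I error is 0.024 to 0.028 against 0.0125, and 0.045 to 0.051 against 0.025.

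**The case against.** The strongest reply is that 10.4.1 never names capsulotomy. The drafters may have meant surgery that confounds the IOP outcome: 10.4.5 uses a similar phrase for secondary surgical interventions, and 8.10 speaks of brief drops for spikes, not of an effect on a washed-out DIOP months later. This stands as a statement about intent. It does not change what the words cover, and without a list an analyst must either apply them literally or decide case by case.

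It is also fair that every rate above is assumed, that the effect is small at 2%, and that 10.4.4 would probably report measured values. Those analyses are exploratory and would not alter the primary test.

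A reader might infer four stronger things that the documents do not support:

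- **That the rule biases one arm against another.** A 5-point imbalance would shift the difference by 0.05 x 8 = 0.4 mmHg. But all arms have cataract extraction, randomisation is stratified by site, and the documents suggest no mechanism for different capsulotomy rates. At q = 5% the chance SE of the rate difference is sqrt(2 x 0.05 x 0.95/137) = 2.6 points, and chance imbalance is already part of the larger SD.
- **That 8.10 reserves treatment failure for IOP-lowering interventions, so that 10.4.1 contradicts it.** Section 8.10 says such subjects are failures; it does not say that no others are. Section 10.4.1 does not label third-criterion eyes as failures.
- **That the rule simply favours the viscoelastic-only arm.** It pulls a true deficit toward zero, but it also lowers non-inferiority power when the arms are equal.
- **That the analysis described as "The survival analysis with the log-rank test for the time to the first ocular hypotensive medications at or after 1 month postoperative" wrongly counts exempt drops.** Section 8.10 exempts post-capsulotomy drops only from the rescue-therapy label, and 10.4.5 is exploratory. At most the two wordings could be aligned.

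**Conclusion.** The concern holds as a defect of wording with a real consequence. The third criterion replaces measured washed-out values with baseline on an open-ended condition. Read with 8.10, its plain terms include Nd:YAG capsulotomy for PCO. That inclusion is an inference from the wording, and redacted text could bear on it, but nothing visible exempts the procedure. No planned sensitivity analysis would show the effect, because 10.4.2 leaves these eyes at zero change.

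That an eye with a genuine reduction is scored as zero follows from the text and needs no assumption. The size does rest on assumptions (mean -8 mmHg, SD 4, equal rates in the arms, capsulotomy unrelated to response). The standardised effect is 0.95, 0.89 or 0.80 of true at 2%, 5% or 10% affected. Hypothesis I loses power. For Hypothesis II, a true deficit is understated, and power falls if the arms are equal. If capsulotomy before month 12 is rare, the practical effect is small.

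**What to change.** Reconcile 10.4.1 with 8.10:

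1. Limit the third criterion to a list of procedures whose IOP effect is expected to persist at the 12-month washed-out DIOP, fixed before unmasked data are seen. Restricting it to procedures done to lower IOP would largely repeat the second criterion.
2. State that Nd:YAG capsulotomy for PCO does not trigger baseline imputation and that the measured washed-out DIOP is used.
3. Add a sensitivity analysis that uses the measured washed-out DIOP for every third-criterion eye that has one.

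The cost is a change of SAP wording and one further analysis, on data already collected. The sponsor must agree a short procedure list before unmasking.

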1 PROTOCOL SYNOPSIS

Protocol Title	A Prospective, Multi-center, Randomized, Controlled, Masked, Post-market Study of use of the OMNI® Surgical System in Combination with Cataract Extraction in Open Angle Glaucoma [REDACTED]
Protocol ID Number	[REDACTED]
Study Device	OMNI® Surgical System
Control Group or Device	[REDACTED]
Study Objective	First, to prospectively compare the clinical effect of the transluminal viscoelastic delivery and trabeculotomy using the OMNI Surgical System to the [REDACTED] used with Cataract Extraction in eyes with open angle glaucoma (OAG) and second, to prospectively compare the clinical effect of the transluminal viscoelastic delivery using the OMNI Surgical System to the [REDACTED] used with Cataract Extraction in eyes with open angle glaucoma (OAG)
Study Design	Randomized, controlled, multi-center, post-market prospective study
Primary Effectiveness Endpoint	Primary inference will be based on a planned analysis when all subjects have completed the 12-month visit. 
 Mean change in unmedicated DIOP from baseline at the 12-month postoperative examination
Other Effectiveness Endpoints	
 Proportion of eyes with a \geq 20% decrease in unmedicated mean diurnal IOP (DIOP) from baseline Proportion of eyes with unmedicated mean DIOP between 6 and 18 mmHg inclusive Mean change in the number of ocular hypotensive medications compared to Screening Percent change in unmedicated DIOP from baseline
Safety Endpoints	
 Rates of ocular adverse events (intraoperative, postoperative) Reduction in best corrected distance visual acuity (BCVA) from baseline (note: reduction in BCVA due to posterior capsular opacity (PCO) will not be treated as a safety event) Secondary Ocular Surgical Interventions, including laser, for IOP control

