Schedule of Visits	Screening, Baseline, Surgery (Day 0), Day 1, Week 1, Month 1, 3, 6, 12, 18, 24, 36 Additional post-washout visits will be scheduled for the subjects who are on medications at 12, 24 and 36 months.
Randomization	1:1:1
Treatments	
 • Ab-interno transluminal viscoelastic delivery (up to 360 degrees) and trabeculotomy (at least 180 degrees and up to 360 degrees) using the OMNI Surgical System • Ab-interno transluminal viscoelastic delivery (up to 360 degrees) using the OMNI Surgical System [REDACTED]

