5 STUDY DESIGN

This is a prospective, randomized, controlled, multicenter, comparative study in which a total of 459 subjects will be randomized in an equal allocation ratio (1:1:1) to either the OMNI (transluminal viscoelastic delivery AND trabeculotomy), OMNI (transluminal viscoelastic delivery only), or [REDACTED] and followed for 36 months after surgery.

The study will employ a medication washout [REDACTED] [REDACTED] which eliminates the potential confounding influence of ocular hypotensive medications in the assessment of device effectiveness.

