8 STUDY PROCEDURES

8.1 STUDY SCHEDULE

8.2 NUMBER OF SUBJECTS, DURATION OF FOLLOW-UP AND STUDY DURATION

Approximately 459 subjects will be randomized (1:1:1) to treatment, [REDACTED]
[REDACTED] No site
will randomize more than 25% of the total number of subjects without prior approval
from Sponsor.

[REDACTED]

Study subject participation will be from approximately 35 months, (at a minimum) to 40 months, depending on the length of the required medication washout prior to baseline and if additional washout is needed [REDACTED] for subjects presenting at these visits with ocular hypotensive medication.

It is anticipated that the enrollment period for the study will last approximately 24 months. Including the 40-month follow-up period, the study is expected to last 54 months.

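### The hypotony criterion for the primary endpoint has no end date, so read literally an IOP below 6 mmHg after Month 12 would replace a measured 12-month DIOP with baseline

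*Combined protocol and SAP*

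**What the plan says.** Section 10.4.1 of the combined protocol and SAP defines the primary analysis and its imputation rule: "The Baseline unmedicated DIOP will be used to impute the 12-month unmedicated DIOP for the subjects meeting any of the following criteria". Because the endpoint is the 12-month value minus the baseline value, an imputed eye has a change of exactly zero.

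The criteria differ in how they are limited in time:

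- Medication that cannot be washed out safely: tied to the 12-month time point.
- Secondary surgery: "Have secondary surgical interventions (such as laser procedure or MIGS) to control IOP before the 12-month washout".
- Other procedures: "Have any ocular procedures that can affect the IOP before the 12-month washout".
- Low pressure: "Have IOP below 6 mmHg at 1 month or later".
- No 12-month washed-out DIOP for any other reason: by its nature a 12-month criterion.

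On timing, the synopsis states: "Primary inference will be based on a planned analysis when all subjects have completed the 12-month visit". Section 5 has subjects "followed for 36 months after surgery", and the synopsis visit schedule runs "Month 1, 3, 6, 12, 18, 24, 36". Section 8.2 adds: "It is anticipated that the enrollment period for the study will last approximately 24 months". The visible text states no per-subject cut of the data at Month 12, and nothing is blacked out in the list of criteria.

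**The concern.** A 12-month endpoint should be settled by what has happened up to 12 months. The low-pressure criterion has a start but no end, and subjects enrolled early will already have Month 18 or Month 24 readings when the last subject reaches Month 12. Suppose an eye falls from 27 to 14 mmHg at Month 12 and then has a recorded IOP of 5 at Month 18. Under the literal wording it is scored as no change at Month 12. An eye with the same course that enrolled late, and has no Month 18 visit yet, keeps its change of -13.

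The planned sensitivity analysis would not show this. The tipping-point analysis in Section 10.4.2 varies only subjects whose 12-month DIOP is missing for reasons outside the first four criteria, and low pressure is the fourth. Those eyes stay at zero throughout. At stake are a primary result that can change with the date of the data cut and, if late low readings are more common in one arm, a biased comparison.

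**Working it through.** **1. The plan's own sample size.** The synopsis gives 411 completers, about 10% dropout and 459 randomized. 411/3 = 137 per arm; 137/0.9 = 152.2, rounded up to 153; 3 × 153 = 459. This reproduces. Since the fifth criterion imputes a missing 12-month DIOP, dropouts remain in the primary analysis, so the number analysed per arm is nearer 153 than 137. Both are carried below.

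**2. Is a limit supplied elsewhere?** Section 8.10 also states the baseline imputation for secondary IOP-lowering interventions, without a time limit; Section 10.4.1 then supplies one. For low pressure, no visible section does.

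**3. Length of enrolment.** Section 8.2 gives about 24 months of enrolment, 40 months of follow-up and a 54-month study. 24 + 40 = 64, not 54; a 54-month total implies 54 - 40 = 14 months of enrolment. Both are used as a range.

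**4. Share with later visits at the primary analysis.** Assume uniform accrual over E months and analysis when the last subject reaches Month 12, ignoring attrition and visit windows. The share past Month v is (E + 12 - v)/E, and not less than 0.

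| | E = 24 | E = 14 |
|---|---|---|
| Past Month 18 | 18/24 = 75% | 8/14 = 57% |
| Past Month 24 | 12/24 = 50% | 2/14 = 14% |
| Past Month 36 | 0% | 0% |

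**5. Effect of one overwritten eye.** The shift in the arm mean is the lost reduction divided by n. For an assumed change of -8 mmHg: 8/153 = 0.052 and 8/137 = 0.058 mmHg. For assumed changes of -6 to -18 mmHg the range is 6/153 = 0.039 to 18/137 = 0.131 mmHg.

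**6. How many eyes?** The documents give no rate, so take an assumed chance p per later visit of a first reading below 6 mmHg. Let s1 be the share that has reached Month 18 only and s2 the share that has reached Month 24 as well. The share overwritten solely because of later readings is q = s1·p + s2·[1 - (1 - p)²]. For E = 24, s1 = 0.25 and s2 = 0.50; for E = 14, s1 = 0.43 and s2 = 0.14.

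| p | q, E = 24 | Eyes per arm (n = 137–153) | Mean shift, 8q | q, E = 14 | Eyes per arm (n = 137–153) | Mean shift, 8q |
|---|---|---|---|---|---|---|
| 0.5% | 0.62% | 0.9–1.0 | 0.05 | 0.36% | 0.5 | 0.03 |
| 1% | 1.25% | 1.7–1.9 | 0.10 | 0.71% | 1.0–1.1 | 0.06 |
| 2% | 2.48% | 3.4–3.8 | 0.20 | 1.42% | 1.9–2.2 | 0.11 |

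If the same analysis were run after everyone had passed Months 18, 24 and 36, q = 1 - (1 - p)³ = 1.5%, 3.0% and 5.9%, and the shifts would be 0.12, 0.24 and 0.47 mmHg.

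**7. Effect on the comparison.**
- Equal q in both arms, overwritten eyes typical of their arm: a true difference d becomes (1 - q)d. With q = 2.48% and d = 1.5 mmHg, the loss is 0.04 mmHg.
- Only one arm affected (the extreme case): the difference moves by the full shift in step 6, 0.03 to 0.20 mmHg, or 2% to 13% of the 1.5 mmHg non-inferiority margin.

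**8. With an upper limit at the 12-month washout.** No eye is overwritten by a later reading, the rule is the same for every enrolment date, and N is unchanged.

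**The case against.** The strongest reply is that the authors meant Month 1 through Month 12. The bullet sits in a list about the 12-month value, and its wording can be read as a lower bound that sets aside early postoperative pressures, which Section 8.10 also treats separately. That intent is plausible and may well be the true one. It is not written, however, and a programmer who follows the list literally could flag later readings.

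A reader might go further and infer that the primary treatment comparison depends on when subjects enrolled. The documents do not support that. Section 8.6 randomizes 1:1:1 within site, so enrolment date is balanced across arms on average; what varies with enrolment is the handling of individual eyes. A reader might also infer a bias against the superiority claim, on the ground that the more effective procedure will produce more very low pressures. The documents give no rates of late low readings by arm, so this remains a possibility.

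Two smaller points also go to the plan. Under Section 19.4 a recorded IOP is already the mean of two or the median of three measurements, and diurnal measurement is specified only at baseline and 12 months, so a trigger based on ordinary IOP at other visits is understandable. The responder and 6–18 mmHg analyses in Section 10.4.4 use available data and could treat the same eye as a success, but they are labelled exploratory, so that mismatch has no inferential weight.

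**Conclusion.** The defect is real on the plain wording: the criterion lacks the end date that its neighbours have, and applied literally it lets an event after the endpoint erase a valid measurement of the endpoint. It deserves correction because it sits in the primary analysis and no planned analysis would expose it.

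The size is probably modest. Under the assumed rates of 0.5–2% per later visit, up to about four eyes per arm are affected. Between-arm bias requires a difference in late low readings by arm; without one, what remains is slight dilution and a 12-month figure that is not fixed at 12 months. Firm support exists for the missing limit and for the presence of post-Month-12 data at the primary analysis. The event rate, the -8 mmHg change and uniform accrual are assumptions, and the range for follow-up shares reflects the inconsistent durations in Section 8.2.

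**What to change.** Amend the fourth criterion in Section 10.4.1 so that it covers IOP readings below 6 mmHg from Month 1 up to and including the 12-month washed-out DIOP, in line with the neighbouring criteria. State that later readings below 6 mmHg are reported only as safety events and do not alter the 12-month value. Make the change before outcome data by arm are seen, so that the limit cannot look like a choice made on the results.

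The cost is a few words. No new data, visits or subjects are needed. A supportive run of the primary comparison using the measured 12-month DIOP for eyes imputed under this criterion, with counts by arm, would be informative. It addresses the separate question of counting low pressure as failure at all, so it is optional and not needed to correct the defect.
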